## **6 SEQUENCE OF PLANNED ANALYSES**

### **6.1 Interim Analyses and Data Monitoring**

No interim analysis will be performed for this study.

Protocol: GHLIP-2-001

Study Sponsor: Golden Biotechnology Corporation

## 6.2 Final Analyses and Reporting

All final planned analyses identified in the protocol and in this SAP will be performed only after the last patient has completed assessments scheduled for the 12-week study period and the database has been cleaned and locked. A blinded data review will be conducted prior to database lock and completion of the final analyses. In addition, no database may be locked, random code un-blinded, or analyses completed until this SAP has been approved.

Key Statistics and study results will be made available to Bestat Pharmaservices Corp. following database lock and prior to completion of the final CSR.

Any post-hoc, exploratory analyses completed to support planned study analyses, which were not identified in this SAP, all be documented and reported in appendices to the CSR. Any results from unplanned analyses will also be clearly identified in the text of the CSR.

## 7 GENERAL CONSIDERATIONS

### 7.1 Relevant SOPs and Policies

The data manager (DM) will carry out verification procedures upon double data entry completion. Data entered in the first database has to be verified against the data entered in the second database for comparison and verification purposes. All discrepancies shall be recorded and data verification output shall be generated after this process. The DM verify the discrepancies between first entry and second entry against the hard copy CRF. All verified data must be uploaded to the updated database(s). Data verification output and relevant records will be stored properly and securely.

To ensure the data reliability, DM validate data based on data validation plan and reconfirm

**Protocol: GHLIP-2-001**

**Study Sponsor: Golden Biotechnology Corporation**

those unreliable values for all collected data includes safety and efficacy data. The locked data will be treated as analyzable data.

## **7.2 Timing of Analyses**

The final analyses will be performed when the last subjects have completed the study or permanently discontinued the study, all queries are solved, protocol deviation/violation has been identified, database has been locked and the statistical analysis plan with detail methods has been finalized and approved.

## **7.3 Missing Data**

Last observation carried forward (LOCF) will be used to approach the missing data of primary endpoint in Intent-To-Treat (ITT) population. For each individual, missing values occurs in efficacy variable (i.e., TG) will be replaced by the later point. If more than two data are missing the following assessment, the last non-missing value will be used to fill in each missing observation. The variable TG related with the primary endpoint assessment will be presented by LOCF method.

No missing data will be imputed for the secondary efficacy or safety analyses.

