3. STUDY DESIGNS

3.1. General Design

This is a multi-center, phase 2, double blind, randomized, placebo-controlled trial of Antroquinonol in patients with hypercholesterolemia and hyperlipidemia. Subjects with a diagnosis of primary hypercholesterolemia (nonfamilial) or mixed hyperlipidemia (TG between 150 mg/dL and 500 mg/dL, and cholesterol between 160 mg/dL and 250 mg/dL or LDL-C > 130 mg/dL) and meet all eligible criteria will be randomized to 4 groups:

1. Antroquinonol 150 mg PO QD
2. Antroquinonol 100 mg PO QD
3. Antroquinonol 50 mg PO QD
4. Placebo

After the end of 12 weeks treatment period, subjects will be followed up for an additional 2 weeks.

Study visits will occur every 4 weeks. During these visits study drug will be administered at the site, new AEs/SAEs as well as follow-up for AEs and SAEs that have not been resolved will be recorded, changes to concomitant medications will be noted, vital signs will be taken, and efficacy evaluations will be performed as well. The studies include collection of biomarker samples, brachial-ankle pulse wave velocity (baPWV) and ankle-brachial index (ABI), E/E', and CT scan of the liver will be performed. The end-of-treatment visit and the last efficacy assessments will occur at week 13 (visit 5) for all subjects. In addition, a 2-week follow-up final visit will be at week 15 (visit 6) in order to collect safety data after the last study drug administration. Subjects will be encouraged to complete all planned visits regardless of their adherence to study drug administration.

Schematic diagram:

The study design (**Figure 3-1**) is shown as follows:

[figure not shown]

Figure 3- 1 Schematic diagram of the study design

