6. STUDY PROCEDURES

This is a, randomized, double-blind, placebo-controlled study composed of the following:

- (1) a screening visit including a wash-out period of 2 weeks will be applied to patients prior to the treatment of Antroquinonol;
- (2) randomization of subjects who meet the eligibility criteria in 1: 1: 1 :1 ratio into the four treatment groups (Antroquinonol 150 mg, Antroquinonol 100 mg, Antroquinonol 50 mg or placebo);
- (3) three on-treatment visits scheduled at four-week interval during which efficacy and safety assessments will be performed;
- (4) and a follow-up visit after the end of treatment, during which safety assessments will be performed.

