9.5. Premature Termination and Missing Values

Subjects may be withdrawn from the study prematurely for lost to follow-up, withdrawal the consent or other conditions as mentioned in Section 4.5.4. The reason of premature termination will be summarized. For drop-out subjects, the listing table will list the detailed reason and date for patients' withdrawals. For subjects who terminate study drug early, values measured after termination of study drug will be censored.

Last observation carried forward (LOCF) will be used to approach the missing data of primary endpoint in ITT population. No missing data will be imputed for the secondary efficacy or safety analyses.

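### SAP 7.3 names LOCF for a missing Week 12 TG, but its working sentences, read literally, give a completer who missed only Visit 5 the off-treatment Day 99 value

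*SAP*

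**What the plan says.** SAP 7.3 treats missing TG in four sentences. The first names LOCF for the primary endpoint in the ITT population. The second says that "missing values occurs in efficacy variable (i.e., TG) will be replaced by the later point". The third says: "If more than two data are missing the following assessment, the last non-missing value will be used to fill in each missing observation". The fourth returns to the start: "The variable TG related with the primary endpoint assessment will be presented by LOCF method".

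The protocol has only one rule. Section 9.5 reads "Last observation carried forward (LOCF) will be used to approach the missing data of primary endpoint in ITT population", and the protocol summary agrees. For subjects who stop study drug early, 9.5 adds that "values measured after termination of study drug will be censored". SAP 7.3 does not repeat that restriction. SAP 12 declares no change from the protocol.

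SAP 7.6 computes the endpoint from Day 85 and Day 1 TG. The documents disagree on whether any TG exists after Day 85:

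- **Lipids drawn at Visit 6 (Day 99):** Protocol 6.1 and SAP 4.1.1 (flow charts, in the efficacy block), Protocol 6.2.4 and SAP 4.1.2.
- **Lipids at Visits 1 to 5 only:** Protocol 7.5.1.
- **Purpose of the visits:** Protocol 3.1 says "The end-of-treatment visit and the last efficacy assessments will occur at week 13 (visit 5) for all subjects". Protocol 6 describes "a follow-up visit after the end of treatment, during which safety assessments will be performed".

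**The concern.** LOCF takes a value from before the gap. The second sentence of SAP 7.3, as worded, takes one from after it. The third sentence makes the last non-missing value a special case, although under LOCF it is the general rule. The only scheduled TG after Visit 5 is at Visit 6, two weeks after the end-of-treatment visit.

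This paragraph is the only imputation rule for the primary endpoint. One programmer working from its middle sentences and another from Protocol 9.5 could derive different Week 12 values for the same patient. If the drug's effect fades after the last dose, the Day 99 value would pull an active arm toward placebo. A choice between the two readings made after unblinding could also look driven by the result.

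**Working it through.** **Step 1. What each reading supplies.** Take the four post-baseline TG samples (Days 29, 57, 85, 99) and list every pattern in which Day 85 is missing.

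| Days with TG observed | Number missing of four | LOCF (before Visit 5) | Next later value |
|---|---|---|---|
| 29, 57, 99 | 1 | Day 57 | Day 99 |
| 29, 57 | 2 | Day 57 | none |
| 29, 99 | 2 | Day 29 | Day 99 |
| 57, 99 | 2 | Day 57 | Day 99 |
| 29 | 3 | Day 29 | none |
| 57 | 3 | Day 57 | none |
| 99 | 3 | none | Day 99 |
| none | 4 | none | none |

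The two readings part in the four patterns with Day 99 observed. The first row is the clearest: one value is missing, so the clause about more than two cannot apply, and the two rules give Day 57 and Day 99. In the row with only Day 99 observed, three values are missing, so the third sentence may compete with the second, and the text does not say which governs.

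**Step 2. Who is exposed.** Protocol 9.5 removes post-drug values for subjects who stop study drug early. That leaves mainly patients who completed treatment, have no Visit 5 sample and do have a Visit 6 sample. Such a patient is possible, because Protocol 3.1 says "Subjects will be encouraged to complete all planned visits regardless of their adherence to study drug administration". Neither document gives a rate.

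**Step 3. Size per affected patient.** Inputs from Protocol 9.2: mean TG reduction 27.5%, SD 40, 30 enrolled per arm. Two assumptions are not in the documents: the carried Day 57 value holds the full 27.5-point effect, and by Day 99 either half or all of it is lost.

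- Shift in an active-arm mean, all lost: 27.5 / 30 = 0.92 points.
- Half lost: 0.5 × 27.5 / 30 = 0.46 points.
- None lost: 0.
- Standard error of a difference between two arms: 40 × √(2/30) = 10.33 points.
- As a share of that: 0.92 / 10.33 = 8.9%; 0.46 / 10.33 = 4.4%.
- Three such patients in one arm: 2.75 points (27%) if all is lost; 1.4 points (13%) if half is lost.

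SAP 5 cites much smaller SDs (2.4% and 5.3%) from a published study. I use 40 because Protocol 9.2 states it as the assumption for this trial. The shares of a standard error depend on that choice; the shifts in points do not.

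**The case against.** The strongest reply is that this is a language slip and nothing more. The paragraph names LOCF at both ends, the protocol names nothing else, and SAP 12 declares no change. Read generously, the middle sentences are a clumsy description of LOCF, in a document whose English is uneven elsewhere. Protocol 3.1 closes efficacy assessment at Visit 5, and Protocol 7.5.1 has no Visit 6 lipids at all, in which case there would be no later value to use. The exposed group is narrow, and no passage describes how fast the effect wears off.

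Much of this stands. A slip is the likelier explanation, and a reader who inferred that the plan deliberately replaces LOCF with a backward fill from Day 99 would go further than the documents allow. The flow-chart rows show that lipids are drawn at Visit 6, not that they are meant to stand in for Week 12.

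The objection does not dispose of the point, for three reasons. Correcting the one word leaves the third sentence redundant or unexplained. Protocol 7.5.1 is outweighed by four other places that schedule Visit 6 lipids. The censoring rule does not reach a patient who finished treatment.

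Two further inferences also fail. Early withdrawals are not the exposed group, since Protocol 9.5 censors their post-drug values. Nor does a patient with both Days 85 and 99 missing go without a value: neither middle sentence supplies one, but the LOCF sentences give Day 57.

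**Conclusion.** The working sentences of SAP 7.3 are wrong as written and conflict with the LOCF rule that the same paragraph and Protocol 9.5 state. The literal consequence, Day 99 in place of Day 57, is confined to patients, mainly treatment completers, who lack a Visit 5 TG but have one at Visit 6. It also depends on Visit 6 lipids being drawn, as most of the schedule says.

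The total effect cannot be derived and is probably small: 4% to 9% of a standard error per affected patient, under the assumed loss of half to all of the effect by Day 99. Those figures are differences between two imputed values, not bias against the unobserved Day 85 value. A reader might infer that the primary result is materially at risk; nothing in the documents supports that. The case for correction is that the primary endpoint needs a single, unambiguous derivation fixed in advance. It should be fixed.

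**What to change.** In SAP 7.3, before database lock:

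1. Delete the second and third sentences of the TG rule (replacement by the later point, and the condition of more than two missing).
2. State that a missing Visit 5 (Day 85 ± 3) TG takes the last non-missing post-baseline TG from before Visit 5, subject to the Protocol 9.5 censoring rule.
3. State that the Visit 6 (Day 99) TG is never used for the primary endpoint.

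A patient whose only post-baseline TG is from Visit 6 will then have nothing to carry forward, and the program should handle that case explicitly. How the early-termination sample in Protocol 6.2.5 fares under the censoring rule is a separate question that this edit leaves untouched.

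The cost is two sentences removed, one or two added, and a matching check in the derivation program. No new data are needed. Because the edit restores the protocol's own rule, it needs no change to Protocol 9.5. SAP 6.2 bars lock, unblinding and analysis until the SAP is approved, which gives a natural deadline.

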6.2.3. On treatment visits (Day 29±3, Day 57±3, Day 85±3)

During the treatment period, subjects will visit the clinic every 4 weeks. Subjects have to come in fasted state for all visits. Therefore, subjects will be instructed not to take study drug in the morning of study visits but to wait until all study assessments have been completed. Subjects will receive new drug supply at each visit and will be required to bring in all unused study drugs for assessment of compliance.

Treatment Period Assessments at Visit 3 and 4 (± 3 days)

The following evaluations will be performed at each visit throughout treatment:

- Physical examination
- Anthropometric measures (Height, weight, waist circumference, BMI)
- Vital signs (pulse rate, body temperature, respiratory rate, and blood pressure)
- Blood samples for
 - lipid profile (total cholesterol, TG, HDL-C, LDL-C and LDL/HDL ratio)
 - serum chemistry (AST, ALT, CPK, BUN, serum creatinine)
- Information on adverse events
- Information on new concomitant medications
- Record of drug dispense and drug return

End of Treatment Assessments at Visit 5 (± 3 days)

The following evaluations will be performed:

- Physical examination
- Anthropometric measures (Height, weight, waist circumference, BMI)
- Vital signs (pulse rate, body temperature, respiratory rate, and blood pressure)
- Blood samples for
 - lipid profile (total cholesterol, TG, HDL-C, LDL-C and LDL/HDL ratio)
 - hematology (WBC, RBC, Hb, Hct, RDW, platelet, MCV, MCH, MCHC, neutrophil-band and segment, lymphocyte, monocyte, eosinophil, basophil)
 - serum chemistry (AST, ALT, CPK, BUN, serum creatinine, albumin, total bilirubin, direct bilirubin, ALP, total protein)
 - biomarkers (hsCRP, IL-1, IL-6, and TNF-alpha)
- 12-lead electrocardiogram
- Brachial-ankle pulse wave velocity (baPWV) and ankle-brachial index (ABI)
- Doppler color flow mapping, and CT scan of the liver for patients with confirmed fatty liver at Visit 2
- Urinalysis
 - routine urine test (pH, protein, glucose, ketone, blood, urobilinogen, bilirubin, nitrite, leukocyte)
 - clinical microscopy
- Information on adverse events
- Information on new concomitant medications
- Record of drug return

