**Protocol: GHLIP-2-001**

**Study Sponsor: Golden Biotechnology Corporation**

Concomitant Therapy	X	X	X	X	X	X
Adverse Event		X	X	X	X	X

\* A wash-out period of 2 weeks will not be applied to patients prior treated with medication which does not affect serum lipid level.

1. Vital signs: pulse rate, body temperature, respiratory rate, and blood pressure (including systolic blood pressure (SBP) and diastolic blood pressure (DBP)).
2. Including height, weight, waist circumference, and BMI (calculated by kg/m^2)
3. Subjects who meet the eligibility criteria will be randomized into treatment arms. If the eligibility is confirmed and a wash-out period is not needed for the subject, based on investigator's judgements the blood test required at V2 can be replaced by the data obtained 14 days before V2.
4. Serum lipids: total cholesterol, triglycerides, HDL-C, LDL-C, LDL/HDL ratio. Serum lipid results obtained 3 days prior to V1 is acceptable.
5. Doppler color flow mapping, and CT scan of the liver. CT scan will not be scheduled at visit 5 on subjects without fatty liver. Results of Doppler color flow mapping and CT scan of the liver obtained between V1 and V2 are acceptable.
6. hsCRP, IL-1, IL-6, and TNF-alpha.
7. WBC, RBC, Hb, Hct, RDW, platelet, MCV, MCH, MCHC, neutrophil-band and segment, lymphocyte, monocyte, eosinophil, and basophil.
8. Biochemical exam: AST, ALT, CPK, BUN and serum creatinine: visit 2 to visit 6; albumin, total bilirubin, direct bilirubin, ALP, total protein: V2, V5 and V6. At screening visit, serum creatinine shall be run for estimating glomerular filtration rate (GFR) and data obtained 3 days prior to V1 is acceptable.
9. Urinary exam: routine urine test (pH, protein, glucose, ketone, blood, urobilinogen, bilirubin, nitrite, leukocyte) and clinical microscopy.

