**Protocol: GHLIP-2-001**

**Study Sponsor: Golden Biotechnology Corporation**

**Every study visit day including Day 1, 29, 57, 85, 99:**

The patient who meets all the entry criteria are eligible for the study. During the study period, the patient have to undergo biochemistry assessment, vital signs measurements, anthropometric measures, physical examination, serum lipid test, concomitant therapy record, and adverse event assessment.

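### TG is carried forward while the other lipids from the same blood draws are not imputed; with withdrawal for lack of response allowed, both results can be biased, and one repeated-measures model could serve all five lipids

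*SAP*

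**What the plan says.** On TG the two documents agree. SAP 7.3: "Last observation carried forward (LOCF) will be used to approach the missing data of primary endpoint in Intent-To-Treat (ITT) population". Protocol 9.5: "Last observation carried forward (LOCF) will be used to approach the missing data of primary endpoint in ITT population". Both then state that "No missing data will be imputed for the secondary efficacy or safety analyses".

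The five lipids are one panel. The flow-chart footnote in SAP 4.1.1 lists "Serum lipids: total cholesterol, triglycerides, HDL-C, LDL-C, LDL/HDL ratio", and SAP 4.1.2 places the serum lipid test under "Every study visit day including Day 1, 29, 57, 85, 99". Protocol 6.2.3 lists the "lipid profile (total cholesterol, TG, HDL-C, LDL-C and LDL/HDL ratio") among the blood samples at Visits 3, 4 and 5.

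SAP 9.3 and 9.4 analyse each lipid by ANCOVA with baseline as covariate, or by Kruskal-Wallis if normality fails. No repeated-measures model appears. SAP 7.6 defines the TG change from Day 1 to Day 85. The planned efficacy tables label both TG and the other lipids as ITT.

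Two further rules matter. Protocol 9.5 says: "For subjects who terminate study drug early, values measured after termination of study drug will be censored". Protocol 4.4 and 4.5.4 (reason 7) allow the investigator to withdraw a patient who does not respond.

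SAP 7.3 also says that "missing values occurs in efficacy variable (i.e., TG) will be replaced by the later point", which runs the opposite way to LOCF. That is a separate wording fault. Here LOCF is taken in its usual meaning.

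**The concern.** No imputation, a week-12 endpoint and censoring of off-drug values together make the analysis of the other lipids, in effect, an analysis of patients who completed on drug. The documents do not use that term; it follows from combining the rules. The TG analysis keeps the same dropouts and treats a Day 29 or Day 57 value as if it were the 12-week result. No reason is given for the difference, so two tables with the same ITT label can describe different patients.

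LOCF recovers the Day 85 difference only under special conditions, for example when the effect is already complete at the last visit before dropout and dropout is unrelated to outcome. A completer analysis needs dropout to be unrelated to outcome. The provision for withdrawing non-responders makes that hard to assume. Gastrointestinal reactions are the expected reactions in Protocol 8.2, so unequal dropout between arms is also plausible, although no dropout rate from them is given. The per-protocol analysis of TG does not test LOCF, because it requires 12 completed weeks and is therefore another completer analysis.

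**Working it through.** **Inputs from the documents.** Protocol 9.2: effect 27.5 points, SD 40, 24 evaluable per group, 20% dropout, 30 enrolled per group.

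**Assumed, not in the documents.** Time course of the effect, split of dropout between visits, correlation 0.6 between visits, and the strength of response-dependent dropout.

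**1. The plan's dropout step.** 24 / (1 - 0.20) = 30 per arm, and 4 × 30 = 120. This reproduces. (The 24 itself does not follow from 27.5 and 40 in a two-sample test, which gives 45 per group. That is a separate matter and does not affect this point.) The other lipids thus rest on about 24 patients per arm and TG on at most 30. Thirty is an upper bound, since the ITT definition requires a post-baseline measurement.

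**2. Cost of losing the dropouts.** The standard error (SE) rises by √(30/24) = 1.118, or 11.8%. The documents give no SD for the other lipids, so take an effect of 27.5/40 = 0.69 SD. Normal-approximation power at two-sided 0.05 is 75.9% with 30 per arm and 66.3% with 24.

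**3. LOCF with random dropout.** Let a and b be the proportions leaving after Day 29 and Day 57, and f29 and f57 the fractions of the effect reached by then. LOCF targets 27.5 × (1 - a - b + a·f29 + b·f57).

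| f29, f57 | a = b = 10% | all 20% after Day 29 | all 20% after Day 57 |
|---|---|---|---|
| 1, 1 (flat) | 27.5 | 27.5 | 27.5 |
| 0.8, 0.9 | 26.7 | 26.4 | 27.0 |
| 0.5, 1 | 26.1 | 24.8 | 27.5 |
| 0.5, 0.8 | 25.6 | 24.8 | 26.4 |
| 0.3, 0.7 | 24.8 | 23.7 | 25.9 |

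The bias lies between 0 and -3.85 points. For 0.5, 0.8 with an even split, 30% and 40% active-arm dropout give 27.5 × 0.895 = 24.6 and 27.5 × 0.86 = 23.7.

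**4. Response-dependent dropout.** Simulation with 400,000 patients per arm, correlation 0.6, and a higher chance of leaving after a poor last value. Overall dropout was 14% to 17% on active and 24% on placebo. The true difference is 27.5.

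| Time course | Completers | LOCF | Likelihood-based (MMRM type) |
|---|---|---|---|
| Flat | 25.2 | 28.3 | 27.3 |
| 50/80/100% | 25.8 | 26.2 | 27.3 |

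LOCF is off by +0.8 or -1.3 points, and completers by -2.3 or -1.7. With no drug effect and the same dropout mechanism in every arm, all three were about zero.

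**5. Precision.** Take 30, 27 and 24 patients at the three visits, SD 40 and equal correlation 0.6. Day 29 explains 0.6² = 0.36 of the Day 85 variance; Days 29 and 57 together explain 2 × 0.6²/1.6 = 0.45.

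- Likelihood-based, variance of a mean in SD² units: 0.55/24 + 0.09/27 + 0.36/30 = 0.03825. SE of the difference: 40 × √(2 × 0.03825) = 11.06.
- Completers: 1/24 = 0.04167. SE: 40 × √(2/24) = 11.55.
- LOCF, counting carried values as full data: SE 40 × √(2/30) = 10.33.

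The variance ratio is 0.03825/0.04167 = 0.918, about 8% lower than completers. Only this ratio carries over to the other lipids. A simulation of 4,000 trials of 30 per arm gave SEs of 11.0, 11.4 and 10.3 in the same order.

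**The case against.** The strongest reply is that the fix does little for TG. With the 50/80/100% build-up and 20% random dropout, effect over SE is 25.6/10.3 = 2.5 for LOCF and 27.5/11.1 = 2.5 for the mixed model, so power is about equal. Root mean squared error is even lower for LOCF: √(10.3² + 1.9²) = 10.5 against 11.1. A 1.9-point bias is under 0.2 SE and works against the drug. All of this stands. The case for change rests on estimating the Day 85 effect under a weaker assumption and on using the same patients for every lipid, not on TG power.

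A reader might infer more than the documents support:

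- **That LOCF does bias TG, or favours the drug.** The bias is zero under a flat effect with random dropout and takes either sign elsewhere.
- **That LOCF creates a false positive.** With no drug effect, a 15-point drift in all arms (5, 10 and 15 by visit) and 30% versus 10% dropout, the expected values are 12.75 and 14.25, a spurious 1.5 points. The 15 is not from the documents. The only control-arm change in Protocol 9.2 is a 0.7% increase, and 1.5 × 0.7/15 = 0.07.
- **That the earlier visits go unused.** The Protocol Summary plans by-visit summaries and ANOVA for other continuous variables, although SAP 9.4 does not repeat this. Nor do all patients have those values, since some may leave before Day 29 or Day 57.
- **That the earlier diarrhea rate (92.31%) predicts dropout here.** Protocol 1.3.1 ties the gastrointestinal findings to a phase I lung cancer study. They support plausibility only.

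Patients who leave before any post-baseline lipid value are helped by neither method. The scenarios also omit the early-termination panel of Protocol 6.2.5, which may be taken on the day of discontinuation and so be later than the carried value assumed.

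**Conclusion.** The concern holds in a limited form. The unequal handling of TG and the other lipids is plain in both documents and unexplained. With withdrawal for lack of response allowed, LOCF can be expected to bias the TG difference, and the completer analysis can bias the other lipids as well as lose patients.

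Size and direction cannot be fixed from the documents. Across the assumed scenarios the LOCF bias was about -4 to +1 points, small against an SE of 10 to 11. The loss for the other lipids is firmer: about 24 instead of up to 30 patients per arm if dropout is the planned 20%. The mixed model's advantage requires data to be missing at random, and its 8% variance gain requires a between-visit correlation near 0.6. This is a worthwhile, low-cost improvement rather than a flaw that invalidates the primary analysis.

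The point does not extend to E/E', baPWV, ABI or liver CT. These are scheduled only at Days 1 and 85 and have no intermediate values to use.

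**What to change.** Revise SAP 7.3, 9.3 and 9.4 and Protocol 9.5 as follows.

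- Analyse percentage change at Days 29, 57 and 85 for TG, total cholesterol, HDL-C, LDL-C and LDL/HDL by one MMRM specification: treatment, visit, treatment × visit, baseline, baseline × visit, unstructured covariance. The Day 85 contrasts are the result.
- For TG, take both the overall Day 85 treatment test and the five Bonferroni-adjusted contrasts of SAP 9.3 and 9.7 from this model, so that the gate and the multiplicity rule stay in place.
- Keep the LOCF ANCOVA, and Kruskal-Wallis if normality fails, as TG sensitivity analyses.
- Apply one rule on which values count as on-drug to all five lipids, and state to which visit an early-termination panel belongs.
- Record the change in SAP 12, which now reports none.

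The cost is wording and programming; no new visits or samples are needed. SAP 6.2 requires SAP approval before database lock and unblinding, so the change should be made by then. The price is a slightly larger TG standard error than under LOCF (about 11.1 versus 10.3), no gain in TG power, and reliance on missing at random.
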